Official title: Prescription of benzodiazepines by Primary health care doctors: characteristics of prescribing trend and implementation of an online educational program

NCT number: not yet assigned

Document date: July 29,2016

Abstract

BZD excessive prescription has long been considered a serious mental health concern in many countries. A large number of interventions using different methodologies have been implemented to change BZD prescription pattern at primary health care settings, with limited positive results.

We aimed to propose the implementation of an effectiveness-implementation hybrid type 1 intervention. In our study we developed an online platform, named ePrimaPrescribe, which was delivered using a Digital Behavior Change Intervention(DBCI).

We included in our study all primary health care units from one region in Portugal which were randomly allocated to receive a Digital Behavior Change Intervention (DBCI) in the format of an online platform to reduce BZD prescription (ePrimaPrescribe) or an online platform concerning communication techniques (control).

We primarily aimed to evaluate the effectiveness of our Digital Behavior Change Intervention (DBCI) using as outcome measure the frequency of BZD prescriptions issued per month. Secondarily we aimed to analyze the effect of ePrimaprescribe on antidepressant prescriptions, to study the effect of ePrimaprescribe on diagnosis definition associated with BZD and antidepressant prescription; to perform a cost analysis considering the monthly National Health Service spending with BZD co-payment. We finally aim to analyze the implementation process using quantitative and qualitative methods.

Ethics and dissemination

This trial was approved by the Ethics Commission for Health of the Regional Administration of Health for Alentejo Region (Portugal) (02/2016(CES) and the Nova Medical School, Nova University Lisbon, Portugal Ethics Commission (47/2016/CEFCM). The results will be submitted for publication in peer-reviewed journals.

Introduction

Benzodiazepines (BZD) are commonly used psychotropic drugs for treating insomnia and anxiety (1). Their long-term use is associated with considerable adverse effects (2), such as increased number of falls and bone fractures (2–4), a higher number of road accidents (2,5), and possible role in inducing the phenomenon of suicide (6–8).

Numerous studies have shown that BZD are still overprescribed and commonly used long-term (9,10), despite the existence of clinical guidance advising the use of non-pharmacological psychological treatments first-line, and to restricting BZD prescription to a maximum of 8-12-weeks.

The consistently high prescription of BZD in Portugal has been the target of references in national and international publications for the last 20 years, with this fact being recognized as a sign of inadequate management of mental disorders and considered a serious public health concern (11). It is also a documented fact that BZD in Portugal

are mostly prescribed in primary health care (12), hence pointing to this setting as crucial to implementation of interventions aiming to change BZD prescription pattern. A large number of interventions using different methodologies have been implemented to change BZD prescription pattern at primary health care settings, such as minimal educational interventions (13–15), systematic discontinuation interventions (16,17), audit and feedback interventions (18), and policy interventions (19,20). The results are inconsistent; when positive, the effect is frequently lost after a short period and seems closely related to each country's primary healthcare setting's particular characteristics.

An educational outreach intervention previously implemented in Portugal had a small effect on BZD prescribing trend and pointed as a primary limitation the lack of staff to implement face-to-face educational sessions to a larger number of General Practitioners (GPs) and with adequate frequency (21). Online interventions, namely targeting a behavioral change, with a low cost and high possibility of wide distribution, were considered a possible way to surpass time and limited resources in primary health care settings to implement an intervention of this nature.

BZD prescription has been reported as a complex behavior influenced by personal values, beliefs, attitudes, experiences, patients' characteristics and demands (22–24). Therefore, besides the relevance of adequately implementing an intervention aiming to change BZD prescription pattern, it is also crucial to gather information about barriers to this implementation, and consider influence factors such as acceptability, practicability, effectiveness, affordability and equity.

This study aimed to evaluate the impact of Digital Behavior Change Intervention tailored online program, ePrimaPrescribe, on changing BZD prescription patterns and, at the same time, to test its implementation in a real-world situation, using an effectiveness-implementation hybrid type 1 design. BZDs are often wrongly chosen to treat anxiety disorder symptoms, at the expense of the adequate pharmacological treatment with antidepressants (25,26). Thus, this study also aimed to verify the effect of our effectiveness trial on antidepressant prescription trends and on diagnoses definition associated with BZD prescription.

Objectives

Main objective

To evaluate the effectiveness of a Digital Behavior Change Intervention (DBCI) at a primary health care setting, in which GPs are given access to an online program, ePrimaPrescribe, aiming to reduce BZD prescription.

Secondary objective

To analyze the effect of ePrimaPrescribe on antidepressant prescriptions.
To study the effect of ePrimaPrescribe on diagnoses registration associated with BZD and antidepressant prescription.
To perform a cost analysis considering the monthly National Health Service spending with BZD co-payment.
To analyze the implementation process using quantitative and qualitative methods.

Methods and analysis

Study design and setting

We choose an effectiveness-implementation hybrid design taking a dual focus a priori in assessing clinical effectiveness and implementation (27).

A hybrid type 1 study tests a clinical intervention, while gathering information on its delivery during the effectiveness trial, and its potential for implementation in a real-world situation.

We performed our hybrid type 1 effectiveness-implementation using as methodology for intervention implementation a two-arm cluster randomized clinical trial. The cluster design was selected because the allocation and intervention were implemented at the healthcare unit level.

The setting for our intervention was primary health care units at a rural region in Portugal, an area of 7393 km², an estimated population of 166 706 inhabitants (2011), a population density of 22.5 inhab./km², and approximately 250 GPs working in primary health care units (of which 110 were included in our study). Portugal has a public accessible national health service, but mental health indicators are alarming (28). BZD prescription in Portugal is very high, as introduced in our background section, and the consumption of these drugs is particularly significant in the region where our intervention was implemented (11).

Eligibility criteria and recruitment

All primary healthcare units from the Portuguese Central Alentejo region were considered eligible. A researcher contacted each healthcare unit coordinator, explained the project's nature, and invited to participation.

The primary inclusion criteria were healthcare units with acceptance of at least 90% of GPs to participate in the study. We chose a higher acceptance rate than usually reported in the literature since we expected, although accepting to participate in the study, a significant number of GPs in each cluster would not actively use the DBCI ePrimaPrescribe platform.

Sample size

The unit of observation for primary analysis was at the individual GP prescription level. Data collected from a previous research implemented in a similar setting (29) allowed performing estimation for sample size (SS) calculation. We started by doing an SS calculation based on all observations' independence and an effect size of 20% reduction. We obtained a total of N=58 participants, N=29 participants per study arm. To adjust for the intra-cluster correlation coefficient (30), we then calculated the design effect (Deff) expressed as:

Deff= 1+r(m-1) - where r denotes the ICC and m is the size for each cluster.

Considering an average cluster of m=5 and an ICC of 0.02, Deff=1.08.

The SS adjusted for ICC was then be given by:

N*= N(1+r (m-1)), so N*=29(1+0.02(5-1)=31.3, hence approximately 32 per study arm.

The number of clusters (k) was given by:

k= N(1+r (m-1))/m, so k=6.4≈ 7

Considering an ICC of 0.02, a 1:1 ratio of allocation of controls per intervention unit, an alpha type error of 0.05, a cluster size of 5 doctors per unit, a minimal difference 20% reduction in the number of BZD prescriptions, the study would have to include 7 clusters per study arm in order to have an 80% power.

Random allocation

Randomization was stratified according to the organizational type of primary health care unit (UCSP vs. USF), the number of GPs per unit, the average number of appointments, and the number of patients per unit per month. We further included in our randomization criteria primary health care unit's proximity, meaning that when distinct units functioned on the same location/building, we allocated them to the same study arm.

In previous research, using similar baseline BZD prescription data from primary health care units, there was a large spread of monthly BZD prescription (29). Since this spread was similar throughout different units, no stratified randomization (or matching for similar prescribing patterns) was considered to be necessary (31).

Healthcare units were included if 90% of the GPs accept participation.

For concealment of allocation, after all eligible healthcare units accepted participation, we allocated them simultaneously to intervention or control group using a computer-generated random number of tables.

The distribution of participants after randomization is presented in the following figure.

[figure not shown]

Figure 1: Distribution of participants after randomization

Blinding

GPs could not be blinded due to the fact that they were asked to participate actively in a study seeking to change their prescription practice. Both GPs included in intervention and control arm were asked to access an online platform. However, they were blinded to the existence of alternative content to the platform presented in their primary health care unit.

The authors were not blinded to primary health care unit allocation.

The primary and secondary outcomes were assessed by analysis of the electronic prescription and diagnosis registration database for each GP. These data were extracted and anonymized (except to primary health care unit identification) by a data manager at the central Shared Services of the Portuguese Ministry of Health, who was not involved in the study and was blinded to participant allocation.

Intervention

Development of Digital Behavior Change Intervention (DBCI) online programs

The online programs were designed based on Behavior Changing Wheel theory (32) theory, considering that behavior change is key to improving healthcare and health outcomes. We used a Digital Behavior Change Intervention (DBCI) mode of delivery. The ePrimaPrescribe program, designed to be implemented in the intervention group, was developed based on guidelines for anxiety and depression treatment and benzodiazepines withdrawal. Our primary sources of information were National Institute for Health and Care Excellence (NICE) guidelines (33), guidelines issued by the Portuguese National Health Directorate (DGS) (34,35), and other relevant literature specifically addressing deprescribing evidence-based practice guidelines (36,37). The program comprised three e-learning modules, each with approximately 30 minutes of duration and with the following subjects: pharmacological effect and clinical use of BZD; how to treat anxiety disorder avoiding the continuous use of BZD; how to manage BZD dependence and BZD withdrawal proposals.

The primary health care units included in the control arm of our study were also offered an online platform, named ComunicaSaudeMental. This DBCI platform's content was developed based on literature concerning general communication techniques and more specific communication techniques for addressing light to moderate mental health disorders or patient's emotional management at primary health care settings. This program comprised (similarly to the one offered to the intervention arm) three e-learning modules, each with approximately 30 minutes.

After the development phase, modules were uploaded to two moodle platforms (one for the intervention educational platform, ePrimaPrescribe; another for the control educational platform, ComunicaSaudeMental), and an individual coded access was created to each participant.

Before the implementation phase, both programs were tested by three GPs and three psychiatrists. Two of the GPs were members of the Primary Health Care Research Department at NOVA Medical School, and one was also a member of the Mental Health Research Department at NOVA Medical School. Two of the three psychiatrists were specialists in substance misuse. These experts were asked to comment on the accuracy and quality of the e-learning modules critically. Their suggestions were carefully considered, and when appropriate, were integrated into the module's final version.

Intervention implementation

We used as guidance to the following intervention implementation report, the Template for Intervention Description and Replication (TIDieR) checklist and guide (38).

ePrimaPrescribe online platform was implemented in primary health care setting since this is where most BZD initial and renovation prescriptions are issued. A Digital Behavior Change Intervention (DBCI) was chosen as the delivery method since we hypothesized that a free, easily accessible platform might have a higher and longer-term effect changing BZD prescription pattern.

Both primary health care units allocated to intervention and control arm had an initial face-to-face visit to present to GPs the online platform, delivery of personal identification access code, explanation on how to access and use it. Informed consent was asked during this initial face-to-face visit.

We expected GPs to start accessing and hence actively participating in the study in the weeks following the first face-to-face visit to their unit. Access to the platform was free, available at any convenient time and frequency, through any digital device with internet connection.

We performed all face-to-face visits to allocated primary health care units in a six-week time frame.

We sent an email to GPs every three months, at three, six and nine months after implementation, as a reminder for participation and as a strategy to improve adherence to the intervention. The platform was not tailored, personalized, adapted, or modified in any way during the intervention implementation period.

To assess how well the intervention was actually implemented, and hence to evaluate the extension to which the intervention was delivered as planned, we performed another face-to-face visit to all participating primary health care units, 12 months after the initial intervention. During this visit, GPs included in the intervention arm were asked to answer a survey exploring their motivations and expectations regarding the use of the ePrimaPrescribe program; a questionnaire for evaluating the barriers and facilitators to the Implementation of the ePrimaPrescribe online platform; and to participate in an exploratory group discussion over the general perception of their study participation and platform implementation.

All face-to-face visits, and hence intervention procedures explanation and monitoring were provided by the first author, who has a background as a psychiatrist and regularly performs her clinical work in the same geographical area where the intervention was implemented.

We performed semi-structured in-depth interviews with an intentional sample of participants from the intervention arm to explore perceptions on the feasibility and implementation of the study.

Outcome assessment

Primary outcome measure

We used as primary outcome measure the frequency of BZD prescriptions issued per month, the proportion of prescriptions issued by participants included in intervention and control units over the study time frame and more specifically at baseline, six and 12 months after intervention.

We included BZDs from the following Anatomical Therapeutic Chemical classification system-coded groups: N05B; N05C and N03AE.

Secondary outcome measures

Effectiveness

We used the frequency of antidepressant prescriptions issued per month, the proportion of prescriptions issued by participants included in intervention and control units over the study time frame and more specifically at baseline, six and 12 months after intervention.

We included antidepressants from the following Anatomical Therapeutic Chemical classification system-coded groups: N06A.

To study the effect of ePrimaprescribe on diagnosis registration, we used the monthly registration distribution of psychological symptoms, complaints, and diagnoses coded at the same month as BZD and antidepressant prescriptions. The GP's diagnosis registration used the International Classification of Primary Care, second edition (ICPC-2) developed and updated by the World Organization of Family Doctors' (WONCA) International Classification Committee (WICC).

We further performed a cost analysis considering the monthly National Health Service spending with BZD co-payment. This cost was compared with the amount that would need to be spent to comply with needs and solutions suggested when evaluating GP's perceptions of the feasibility and implementation.

Implementation

We studied the implementation process using quantitative and qualitative methods.

Quantitative data

We developed a standardized onsite survey aiming to explore the following themes: GP's self-evaluation of knowledge about the management of patients with anxious and depressive symptomatology; reasons for prescribing BZDs and antidepressants; subjective assessment of the amount of BZDs and antidepressants prescribed; reasons for keeping long-term BZD prescription; difficulties for changing long-term BZDs prescription; the degree of concern with continued BZD prescription; knowledge and degree of adequacy of the existing Portuguese guidelines on BZD prescription; motivations and expectations regarding the use of the ePrimaPrescribe program in clinical practice and participation in the study. This questionnaire had 18 multiple questions and 14 short answer questions. The development and testing of this questionnaire is detailed in Part 5, section 1.

We adapted the Barriers and Facilitators Assessment Instrument (BaFAI)(39) to the implementation of the DBCI ePrimaPrescribe program. This questionnaire is organized into four categories: barriers deriving from the characteristics of the practice/innovation; barriers deriving from the characteristics of the professionals; barriers due to patient characteristics; barriers arising from the intervention context. It has twenty-five questions of a five-point Likert scale type.

We asked all participating GPs to complete the onsite survey and BaFAI questionnaires at the end-of-study face-to-face visit that was performed after completion of the twelve-month intervention period.

At the end-of-study face-to-face visit, we also collected GPs sociodemographic data.

Qualitative data

During our end-of-study face-to-face visit, we performed a group discussion in each primary health care unit included in the intervention group, to explore GP's perceptions over their participation.

We finally performed semi-structured in-depth interviews with an intentional sample of participants from the intervention arm to explore perceptions of the study's feasibility and implementation. The interview guide structure was developed after an exploratory analysis of the themes emerging from the answers to the onsite survey questionnaire, from the answers to the BaFAI, and from the group discussion occurring during the end-of-study visit.

Data management

Each prescription data was coded using an individual GP and patient numerical identification, in a secured and validated electronic database, directly extracted by the central Shared Services of the Portuguese Ministry of Health.

Data concerning clinical diagnosis was extracted by the same method as the prescription database. Matching of prescription and diagnosis database was

performed using the coded patient's numerical identification and prescription/diagnosis registration month.

Data obtained through questionnaires and interviews was collected after participants signing an informed consent during the initial implementation face-to-face visit.

Statistical analysis

We performed an exploratory descriptive analysis using number of prescriptions as primary measure of outcome, considering as main influencing factors the patient's age and sex, by units of intervention and control.

We performed most analysis at the level of intervention versus control clusters (so compared together the set of intervened units vs the set of control units), since the available data did not allow for the author to identify each of the participating GP, hence also not allowing to distinguish in the intervention units, which GPs were compliant with the intervention (i.e. the doctors that actually used the DBCI), from those that, although initially agreeing to participate, finally didn't use the platform.

We tested for significant differences among the baseline characteristics of the intervention and control group. We performed descriptive analysis, with continuous variables summarized using means and standard deviations for normal distributions, and by medians and the 25th and 75th percentiles for non-normal distributions.

Estimated effects were calculated by comparing number of prescriptions in the intervention and control groups at baseline, six months, and 12 months after intervention.

All analyses were performed on an 'intention-to-treat' basis (i.e., all initially enrolled GPs were included in the analysis according to the group to which they were assigned). This approach reduces the bias that may occur when participants not receiving assigned treatments are excluded from analysis.

The intervention and control groups were compared at the defined time points accounting for clustering by unit.

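### Stratifying some 14 to 22 units on four characteristics, with no blocking or constraint described, cannot be relied on to balance unit size or give 1:1 allocation, and no adjustment is planned

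*Combined protocol and SAP*

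**What the plan says.** The Random allocation section of the combined protocol and SAP lists four stratification factors: "Randomization was stratified according to the organizational type of primary health care unit (UCSP vs. USF), the number of GPs per unit", then "the average number of appointments, and the number of patients per unit per month". Unit type has two levels. The other three are size or workload measures, given without cut-points. A separate rule covers shared premises: "when distinct units functioned on the same location/building, we allocated them to the same study arm".

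The next paragraph refers to the spread of monthly benzodiazepine prescribing in an earlier study, and concludes that "no stratified randomization (or matching for similar prescribing patterns) was considered to be necessary".

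The only mechanism given is that, once all eligible units had accepted, "we allocated them simultaneously to intervention or control group using a computer-generated random number of tables". No block size, minimisation or restricted list is mentioned.

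The Sample size section assumes "a 1:1 ratio of allocation of controls per intervention unit" and concludes that "the study would have to include 7 clusters per study arm in order to have an 80% power". Study design and setting reports 110 GPs included. The text does not give the number of units randomised. It may be in Figure 1, which is not available here.

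The primary outcome is a monthly count of prescriptions. A proportion is also mentioned, but its denominator is not defined. The Statistical analysis section compares counts between arms at baseline, six and 12 months and accounts for clustering by unit. It names no denominator such as list size or appointments, and no adjustment for the four stratification factors.

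**The concern.** Stratification balances arms only where a stratum holds at least two units and something forces those units to be split. Four crossed factors spread over so few units leave many strata with one unit, and that unit goes to either arm by chance. Without blocking, even strata with several units are not balanced.

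A prescription count depends on how many patients a unit has and how many appointments it gives. If one arm receives more or larger units, the raw comparison mixes unit size with the intervention effect, and the described analysis has no term to separate them. The 1:1 allocation behind the sample size is also not secured. All units were known before allocation and were allocated together, so balance could have been built in at little cost.

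**Working it through.** **The plan's own figure (Sample size section)**
- Design effect = 1 + 0.02 × (5 − 1) = 1.08.
- Adjusted size = 29 × 1.08 = 31.32, rounded up to 32 per arm.
- Clusters = 32 / 5 = 6.4, rounded up to 7 per arm, so 14 in total. This reproduces the plan.

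**Number of units**
- Planned minimum: 2 × 7 = 14.
- Implied by the GPs included, if the planned mean cluster size held: 110 / 5 = 22. This is an assumption.

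**Number of strata**
- Every factor in two levels: 2⁴ = 16, the fewest possible.
- The three size measures in three levels: 2 × 3³ = 54.

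**One-unit strata** (simulation, 5,000 runs per setting; unit type split about 50:50; size measures with correlations of 0, 0.7 and 0.9, cut into equal groups)

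| Units | Strata | One-unit strata | Share of units in them |
|---|---|---|---|
| 14 | 16 | 3.5 to 6.8 | 25-49% |
| 22 | 16 | 3.9 to 6.1 | 18-28% |
| 14 | 54 | 7.4 to 11.9 | 53-85% |
| 22 | 54 | 8.6 to 16.1 | 39-73% |

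With 16 strata, one-unit strata are about half or more of those occupied: 3.5 of 7.0 to 6.8 of 10.2 at 14 units, and 3.9 of 8.4 to 6.1 of 12.7 at 22.

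**Split of units between arms, unrestricted table** (exact binomial, probability ½ per unit)
- 14 units: P(7:7) = C(14,7) / 2¹⁴ = 3432 / 16384 = 0.21. Any other split leaves one arm below 7, so P(an arm below 7) = 1 − 0.21 = 0.79.
- 22 units: P(difference of 4 or more) = 1 − [C(22,11) + 2 × C(22,10)] / 2²² = 1 − (705432 + 2 × 646646) / 4194304 = 0.52.
- 22 units: P(an arm below 7) = 2 × [C(22,0) + … + C(22,6)] / 2²² = 2 × 110056 / 4194304 = 0.05.

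**Stratified and constrained allocation** (simulation; 16 strata, size-measure correlations 0.3 to 0.7, no shared-building grouping; constrained means one of the best 10 of 100 random equal-size allocations)

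| Quantity | Units | Unrestricted table | Blocks of two in strata | Constrained |
|---|---|---|---|---|
| Arms differ by 4 or more units | 22 | 52% | 24-27% | 0% by construction |
| Some size measure differs by more than 0.5 SD | 22 | 49-60% | 22-34% | about 0.1% or less |
| Some size measure differs by more than 0.5 SD | 14 | 67-77% | 46-65% | 1-7% |
| An arm has fewer than 7 units | 14 | 79% | 67-71% | 0% by construction |
| An arm has fewer than 7 units | 22 | 5% | under 0.1% | 0% by construction |

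With 54 strata and 22 units, blocks of two give a difference of 4 or more units in 34-46% of runs (correlations 0 to 0.9). Keeping shared-building units together reduces the number of independent allocations further. It can also prevent an exactly equal split, so the zeros need not hold once that rule is applied.

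**The case against.** The plan says the randomisation was stratified. A random number table is only a source of randomness and is compatible with blocks within strata or a restricted list. A reader might infer that the scheme cannot give balance or 1:1 allocation. The text does not support that: either can arise by chance, and simultaneous allocation leaves room for a restricted procedure that is simply not described. The unrestricted-table figures should therefore be read as the unfavourable end. On the favourable reading, blocks of two, both risks at 22 units are roughly halved. They do not disappear.

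A reader might also infer a loss of power. At 22 units this is slight: a 13:9 split keeps 4 × 13 × 9 / 22² = 468 / 484 = 0.97 of the efficiency of an equal split and still leaves at least 7 per arm. The 7-per-arm risk is serious only near 14 units, where 110 GPs would mean 110 / 14, or about 8 per unit, rather than the planned 5.

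A third inference is that the section contradicts itself by claiming stratification and then calling it unnecessary. The second statement follows from a remark on prescribing spread, and its parenthesis is about prescribing patterns. It plausibly concerns baseline prescribing level only, so it is a wording problem. Shared location is likewise a same-arm rule, not a fifth stratification factor.

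Finally, unit numbers, cut-points and correlations are assumed, and the actual split may be in Figure 1. Nothing here shows that the arms were in fact unbalanced. These limits stand, but none of them supplies a balancing mechanism or an adjustment.

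**Conclusion.** The point holds as a weakness of design and analysis; it is not proof of imbalance. With at least 16 strata for about 14 to 22 units, and no restriction described, the scheme cannot be relied on to balance unit size and workload or to give equal numbers of units.

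At 22 units with two-level factors, even the favourable reading leaves about a one-in-four chance that the arms differ by 4 or more units, and a 22-34% chance that some size measure differs by more than 0.5 SD. The shortfall below 7 units per arm is secondary: large near 14 units, about 5% or less at 22. The finding that many strata hold one unit survived every combination of cut-points and correlation tried, but the percentages depend on those assumptions.

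The consequence is material because a raw count is compared with no stated adjustment for the factors used in randomisation. It should be corrected.

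**What to change.** **Allocation.** Replace the four-way stratification with covariate-constrained randomisation of location groups:
- List the allocations that keep shared-building units together and give equal, or closest possible, numbers of units per arm.
- Score each on unit type and the size measures.
- Draw one at random from the best-balanced set, for example the best 10%.

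**Analysis.** Adjust the primary comparison for the variables used in randomisation. The three size measures overlap and clusters are few, so unit type plus one size measure, or a size offset, may be enough.

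**If allocation is already done**, as the past tense suggests, state the procedure, cut-points and number of location groups actually used, and make the analysis adjustment.

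**Wording.** Reword the sentence on stratification being unnecessary to say that it refers to baseline prescribing level, if that is what is meant.

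**Cost.** One short script run once, and a few sentences of text. The constrained set must be checked so that no two units are always or never together, apart from those sharing a building. With 14 units there are 3432 equal splits before that grouping, so the best 10% is about 343; grouping will reduce this. Adjustment costs a few cluster-level degrees of freedom: a two-arm comparison of 14 units has 14 − 2 = 12, falling to 10 with two unit-level covariates and 8 with four. At 22 units the figures are 20, 18 and 16.
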